#### **Physical Activity Measurements:**

**Resting heart rate:** Participants will remain in a seated position for a miminium of 15 minutes prior to resting heart rate being taking with a Omron Professional Digital blood pressure and heart rate monitor.

**Three minute stair step**: Queens College Step Test: The Queens College Step test is one of many variations of step test procedures, used to determine aerobic fitness. Compared to the Harvard Step Test, this version has a lower step height, slower cadence, shorter test and more simple analysis (33).

**Pedometer data**: We will compare average steps per week at 14 weeks relative to baseline steps assessed in the first 2 weeks. After 14 weeks, we will assess the percentage of participants that attain a weekly goal of 10,000 steps daily for greater than 3 out of 7 days of the week. While we know of no validated reference for this, this goal was discussed with [name], FAHA, FACSM who is Director, Human Performance Research & Lifestyle Interventions for Veterans (LIVe) Veterans Affairs Medical Center, DC.

**Nutrition/Activity Questionnaires (Appendix I)**: Starting The Conversation (STC) is an eightitem simplified food frequency instrument designed and validated for use in primary care and

Page 10 of 14

health-promotion settings (34).

**Physical activity (Appendix J)**: The International Physical Activity Questionnaire (short) is a validated questionnaire that reviews the last 7 days of activity for middle aged adults (age 15-69 years) (35).

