### Inclusion criteria:

- 1. Age 18-55
- 2. Prediabetes (A1c 6.0-6.4) or Diabetes (A1c 7.0-10)
- 3. BMI ≥ 30 kg/m2
- 4. Willing to wear pedometer during study period
- 5. Able to walk 2 city blocks at baseline without assistance (self-reported)
- 6. Reading level at least 6th grade in English
- 7. Expected to remain in local community for at least 4 months

Page 6 of 14

- 8. Either is not treated with or has been on a stable treatment regimen of any of the following medications for a minimum of 3 months prior to Visit 1 (Screening/Enrollment):
  - a. Sulfonylureas
  - b. Biguanidine
  - c. Thyroid replacement therapy
  - d. Glp-1 agonists
  - e. Sodium-glucose co-transporters
  - f. Basal insulin
  - g. Thiazolidinediones
  - h. Hormone replacement therapy (female subjects) estrogen/progesterone products
  - i. Oral contraceptives/birth control (female subjects)
  - j. Antidepressant agents (SSRIs, Paxil, Prozac, Celexa, Zoloft, etc.)
- 9. Is able to read, understand, and sign the Informed Consent Form (ICF) and if applicable, an Authorization to Use and Disclose Protected Health Information form (consistent with Health Insurance Portability and Accountability Act of 1996 [HIPAA] legislation), communicate with the investigator, and understand and comply with protocol requirements

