https://www.diabetesprevention.pitt.edu/index.php/for-the-public/for-health-providers/grouplifestyle-balance-curriculum. In this study, we will offer an adapted brief-intervention DPP in the first meeting. Our intent in providing this material is to support a primarily *self-directed* diet, activity and weight behavior modification context for use of the RT-CGM. Our diabetes educator will be responsible for reviewing the DPP materials and fat, calorie and activity goals at their original session along with materials developed about what different foods and activity does to your blood sugars prior to the initial use of RT-CGM. We reviewed the educational materials and handouts from the 12 sessions and consolidated them into a 12 page handout which was also reviewed by the current director of The Diabetes Prevention Support Center/DPP Lifestyle Resource Core at the University of Pittsburgh. Consistent with social cognitive theory, all participants are given fat and calorie goals based on their initial weight upon enrollment and an

Page 9 of 14

activity goal of 150 minutes of activity weekly with ongoing goal to 300 minutes weekly. They are asked to self–monitor weight, food intake and physical activity levels with goal of 7% weight loss (32).

**Measurements (Appendix C)**: We will measure HbA1c at the beginning of the study period and at 14 weeks. At each visit, blood pressure, weight, height, and waist circumference will be measured. At baseline and 14 weeks, questionnaires on diet and physical activity and selfperception questionnaires will be obtained. In the intervention group at 14 weeks, a questionnaire about CGM technology and perception of benefit of CGM use will be obtained, for diabetics and for prediabetics. Body composition will also be assessed serially by bioelectrical impedance using a Tanita scale at baseline and 6 weeks and 14 weeks. Pedometer data will be downloaded at 2 weeks, 6 weeks and 14 weeks. Physical fitness testing by resting heart rate and three minute stair step (amount of/change in steps climbed in 3 minutes) will also be obtained at baseline and 14 weeks.

**Anthropometrics: Height** will be recorded in centimeters and inches by a Stadiometer. **Weight** will be recorded in pounds and kilograms using a SECA Digital scale. **Waist circumference** will be meaured using a flexible measuring tape, and **blood pressure** taken with an Omron Professional Digital blood pressure machine.

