### Collection of Human Biological Specimens:

**Fingerstick and serum HbA1c**: The HbA1c test is a blood test that provides information about a person's average levels of blood glucose over the last 3 months. The DCA Vantage Analyzer HbA1c assay tests for a quantitative determination of HbA1c in human whole blood, and provides immediate test results from a finger prick of blood. Serum HbA1c is sent via LabCorp. Urine HCG: HCG by urine dipstick will be collected prior to enrollment in study, if applicable. **Serum fasting lipids** will be collected at baseline and 14 weeks. This data will be provided to the participant to discuss further with their physician at the completion of the study when both pre and post labs are available.

**Perception of CGM (Appendices Q and R):** The Harvard Joslin Diabetes Center has developed a series of questionnaires on CGM experiences, opinions and expectations that will be given at the end of the intervention and has been adapted for the prediabetes population as well.

**CGM Data /Evaluation Measures:** Compliance/duration of participants with wearing CGM will also be recorded. Glucose dynamics, e.g., standard deviation, mean amplitude of glucose excursion (MAGE), and other statistical measures of glucose variability in those with prediabetes/diabetes/obesity with be reviewed from the CGM device data at baseline 2, 6 and 14 weeks

**Self perception/psychosocial questionnaires (Appendix K):** The Weight Efficacy Life-Style Questionnaire (WEL), Eating Habits and Exercise Confidence questionnaires will be given to patients at the beginning and end of the study to help evaluate any changes in self-perception after intervention (36-38).

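### The 10,000-step percentage is taken only after week 14, and steps per week has no wear-day rule, so neither step summary on its own shows a change in activity cleanly

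*Protocol*

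**What the plan says.** Activity level is one of the Aim 1 outcomes. The pedometer paragraph (Protocol, Physical Activity Measurements) plans two step summaries.

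- **Continuous:** "We will compare average steps per week at 14 weeks relative to baseline steps assessed in the first 2 weeks".
- **Attainment, at the end of the study only:** "we will assess the percentage of participants that attain a weekly goal of 10,000 steps daily for greater than 3 out of 7 days". The paragraph adds "While we know of no validated reference for this" and refers to a discussion with an outside expert.

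On who enters and how wear is handled:

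- The inclusion criteria ask for a minimum walking ability, "Able to walk 2 city blocks at baseline without assistance (self-reported", and for "Willing to wear pedometer during study period". Neither the inclusion nor the exclusion list caps baseline activity.
- Wear is tracked for the glucose sensor: "Compliance/duration of participants with wearing CGM will also be recorded". Nothing equivalent is said about the pedometer, and no valid day, minimum number of days or handling of missing days is defined.

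On timing, the Measurements paragraph under Study Procedures says "Pedometer data will be downloaded at 2 weeks, 6 weeks and 14 weeks". The section Weeks 2, 6 gives collection at weeks 6 and 14 only. The Week 14 section has participants go on wearing the pedometer after that visit and then mail it back.

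The SAP does not mention pedometer data. It takes the time main effect as the effect of interest for every outcome.

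**The concern.** A percentage measured once, at the end, mixes people who became active with people who always were. With 30 and 15 participants, one person who met the criterion at entry is worth 3.3 points in the RT-CGM group and 6.7 points in the control group. The SAP reads each outcome over time, and this percentage has no earlier value to be read against.

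Steps per week does have an earlier value, but a weekly total depends on how many days the device was worn as well as on walking. If wear differs between the first two weeks and week 14, or between arms at week 14, that difference is read as a difference in activity. It could hide a real gain or suggest one that did not happen.

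**Working it through.** The documents give no step mean, SD, attainment rate or wear rate, so there is no planned figure to reproduce. The steps below use the group sizes in the protocol (30 RT-CGM, 15 control) and assumptions marked as such.

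**1. Weight of one person.** 1/30 = 3.3 points; 1/15 = 6.7 points.

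**2. How many meet the criterion at entry (assumed inputs).** More than 3 of 7 days means at least 4. Simulate 400,000 people with a normal person mean (truncated at 0) plus normal day-to-day variation over 7 days, and count those with at least 4 days at 10,000 or more.

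| Mean steps/day | Between-person and day-to-day SD (each) | Meet at entry | Expected of 15 | Expected of 30 |
|---|---|---|---|---|
| 5,500 | 2,000 | about 2% | 0.3 | 0.6 |
| 4,500 | 2,500 | about 2% | 0.3 | 0.7 |
| 5,500 | 2,500 | about 5% | 0.8 | 1.5 |
| 6,500 | 2,500 | about 10% | 1.5 | 3.1 |
| 6,500 | 3,000 | about 14% | 2.2 | 4.3 |
| 7,500 | 3,000 | about 22% | 3.4 | 6.7 |

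The range runs from less than one person per arm to about 3 controls and 7 RT-CGM participants.

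**3. What the week 14 figure cannot separate.** Suppose 30% attain the criterion at week 14. If 30% met it at entry, the change is 0 points. If 10% did, it is +20 points. The planned report is 30% in both cases.

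**4. Noise in the arm comparison.** Let nobody change, and let attainers in the two arms be independent binomials (30 and 15) with the same rate. The exact chance of an arm gap of 20 points or more is 1.3% at a rate of 5%, 5.2% at 10% and 14.6% at 20%. The expected gap is zero in each case.

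**5. Non-wear and steps per week.** If unworn days enter as zero, weekly total = steps per day × days worn. At an assumed constant 7,000 a day:

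- 7 days: 49,000
- 6 days: 42,000 (−14.3%)
- 5 days: 35,000 (−28.6%)

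A true 20% gain with wear falling from 7 to 5 days appears as 1.2 × 5/7 − 1 = −14.3%. No change with wear rising from 5 to 7 days appears as 7/5 − 1 = +40%. The mean per worn day is 7,000 throughout.

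**6. Non-wear and the percentage.** If each worn day has an assumed 60% chance of reaching 10,000, P(at least 4 such days) is 71% with 7 days worn, 34% with 5, 13% with 4 and 0 with 3.

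**7. Whether the baseline data will exist.** The Measurements paragraph has a week 2 download; the section Weeks 2, 6 does not. Without it, the first two weeks may not be separable from what follows. The text also leaves open whether the week 14 figure uses days before the visit or the wear period after it.

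**The case against.** **Change is already measured.** The sentence just before the attainment criterion compares steps with baseline, and the activity questionnaire, resting heart rate and step test are planned at both times. This stands: the attainment percentage is a supplement, and a reader who inferred that the whole Aim 1 activity result is compromised would go too far.

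**Randomization protects the arm comparison.** This also stands. A reader might infer that baseline attainers bias RT-CGM against control; in expectation they do not. The weakness lies in reading the raw percentage as change, and in precision.

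**Loss of wear is assumed.** No document says that unworn days count as zero, that wear declines by week 14, or that RT-CGM users wear their devices more. What remains is that no wear rule is stated, so the plan does not prevent these problems.

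**The entry rate may be negligible.** All participants have a BMI of at least 30, and lower step inputs give about 2%. This stands as a limit on size. It does not rescue the percentage, because only the baseline value can show whether the rate was negligible.

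**A mismatch with the coached goal?** One might also object that participants are set an "activity goal of 150 minutes of activity weekly with ongoing goal to 300 minutes weekly" and are scored on steps. The documents do not make this an error. The protocol's section on risks describes the recommended exercise as brisk walking or jogging, which a pedometer counts. The handout in Appendix B is not shown and may contain a step goal. The lack of a validated reference is disclosed. A second threshold that differs from the coaching target is a matter of preference.

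**Conclusion.** The point holds in a limited form. As written, the week 14 percentage cannot show a change in activity, because it has no baseline counterpart and entry does not screen out people who already meet the criterion. This follows from the text and needs no assumption. Its size does need one: about 2% to 22% meeting the criterion at entry, under step means of 4,500 to 7,500 a day and SDs of 2,000 to 3,000, none of which the documents supply.

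For steps per week, the finding is the missing wear rule. The loss of 1/7 for each unworn day in a week holds only if totals are used as recorded. The conflict over the week 2 download is plain from the text and matters because both step summaries, once repaired, depend on those baseline data.

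The consequence is confined to the two pedometer summaries in a 45-person pilot. It is worth correcting because the correction is cheap.

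**What to change.** 1. Apply the same criterion to the first-two-weeks data, with a rule for reducing two weeks to one 7-day assessment. Report attainment at both times by arm.
2. Compare arms at week 14 adjusted for baseline attainment or baseline steps. Give the difference with an interval; with so few attainers, adjusting for baseline steps may be the more stable choice.
3. Replace steps per week by mean steps per worn day. State what makes a day valid (for instance, treating near-zero counts as not worn) and how many valid days are needed, and show the number of worn days by arm and time. Apply the same valid-day rule to the attainment percentage.
4. Reconcile the section Weeks 2, 6 with the Measurements paragraph so that the week 2 download is certain. State which days form the week 14 window.
5. Optionally, add the percentage reaching 150 minutes a week from the activity questionnaire, and from the fitness log if it records minutes.

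The cost is wording and a little more analysis, on data already planned provided the week 2 download takes place. The attainment figure may look less favourable once baseline attainers are shown.

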### Collection of Human Biological Specimens:

**Fingerstick and serum HbA1c**: The HbA1c test is a blood test that provides information about a person's average levels of blood glucose over the last 3 months. The DCA Vantage Analyzer HbA1c assay tests for a quantitative determination of HbA1c in human whole blood, and provides immediate test results from a finger prick of blood. Serum HbA1c is sent via LabCorp. Urine HCG: HCG by urine dipstick will be collected prior to enrollment in study, if applicable. **Serum fasting lipids** will be collected at baseline and 14 weeks. This data will be provided to the participant to discuss further with their physician at the completion of the study when both pre and post labs are available.

**Perception of CGM (Appendices Q and R):** The Harvard Joslin Diabetes Center has developed a series of questionnaires on CGM experiences, opinions and expectations that will be given at the end of the intervention and has been adapted for the prediabetes population as well.

**CGM Data /Evaluation Measures:** Compliance/duration of participants with wearing CGM will also be recorded. Glucose dynamics, e.g., standard deviation, mean amplitude of glucose excursion (MAGE), and other statistical measures of glucose variability in those with prediabetes/diabetes/obesity with be reviewed from the CGM device data at baseline 2, 6 and 14 weeks

**Self perception/psychosocial questionnaires (Appendix K):** The Weight Efficacy Life-Style Questionnaire (WEL), Eating Habits and Exercise Confidence questionnaires will be given to patients at the beginning and end of the study to help evaluate any changes in self-perception after intervention (36-38).

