GW Medical Faculty Associates Internal Medicine clinic, Gynecology clinic, and Endocrine clinic by medical staff and provider flier (Appendix F). Information about the study will be made available to those patients by a Study Flier (Appendix H) which will provide them with contact information for the study coordinator. As well, if potential participants express interest in the study to medical staff at GW, permission for the study coordinator to contact them via telephone or email will be requested and potential participants will be contacted for further screening and potential enrollment. The Study Screening and research procedures will take place at the GW endocrine clinic. Subjects may also be identified through posters and flyers placed in the GW community. Potential subjects who satisfy the study criteria and express interest in the study will be given information about participation either by mail, email or a phone call, depending on their preference. Pre-screening questions will be asked but no study related procedure or screening questions will be performed until informed consent/authorization have been obtained (see Appendices D and L).

We propose to perform a prospective study of 45 participants that will involve 15 subjects (ages 18-55) who are obese (BMI>30) and have prediabetes with HbA1c 6.0-6.4%, and 15 obese (BMI>30) subjects with Type 2 diabetes (ages 18-55) and with HbA1c 7.0-10.0%. 15 subjects will be in the control group with either prediabetes (n=7) or diabetes (n=8). Subjects will be randomized to intervention or control through a computer-generated system. All eligible participants will be able to walk 2 city blocks at baseline. Patients with prediabetes will be on no medications for diabetes and patients with Type 2 diabetes will have to be on the same diabetes medication(s) for 3 months prior to enrollment. The medication regimen may include basal insulin but not premeal insulin. Uncontrolled diabetes A1c>10.1% will be excluded, as well as participants who are pregnant, lactating, enrolled in another weight loss program, or using a weight loss medication (see inclusion /exclusion criteria below). The study will be advertised by flyers in the GW Endocrine Clinic, Internal Medicine Clinic, and also advertisements in the local newspaper.

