### Study Design (see Appendix C):

#### Screening/Pre-Intervention Visit:

Consent will be obtained prior to any screening procedures being completed, and conducted in a quiet room. Participant will be given ample time to ask questions, and a copy of the signed consent form will be given prior to start of screening visit.. Participants will fill out a contact form, including emergency contact. Study staff will review medical history and medications (through appendix E), as well as all inclusion/exclusion criteria. Vital signs will be collected, including height, weight, blood pressure, waist circumference, and resting heart rate. Body composition will also be assessed by bioelectrical impedance using a Tanita scale. A urine pregnancy test (if applicable), lipid panel, and HbA1c, both point of care (fingerprick) and serum, confirmed via LabCorp, will be obtained to determine prediabetes or diabetes. Approximately 1 teaspoon of blood will be drawn. (Note: 10 hour fasting labs will be required for Weeks 0 and 14. If the patient is not fasting, they can return the next day for fasting labs.) If a patient has an HbA1c documented in the medical record within 2 weeks of the pre-intervention session, then the point of care HbA1c will not be done. The available A1c will be used. If they meet all inclusion and exclusion criteria (as outlined above), they will be randomized into either the CGM intervention or control arm at the screening visit.

At the pre-intervention session (week 0) the control and CGM intervention groups (composed of both diabetics and prediabetics) will be asked to wear the CGM blinded for 10 days. They will be asked to continue their usual diet and activity and observe and record their physical activity and food intake on appropriate logs. They will be given a pedometer to track physical activity data, and be given other self-report questionnaires on their perception of CGM, physical activity, and nutrition. The 3-minute stair step test will be conducted. Week 0 consenting and baseline data/measurements will take between 1 hour 30 minutes to 2 hours.

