#### Weeks 2, 6

RT-CGM education and use will be coupled to one initial nutrition and exercise counseling session at Week 2 by the diabetes educator. Individually administered nutrition and exercise counseling will be based on a condensed version of the standard 12-session Diabetes Prevention Program Group Lifestyle Balance (DPP GLB, Appendix B) material and received by all participants. All those enrolled in the CGM intervention (N=30) will participate in 2 cycles of RT-CGM with direct feedback on CGM patterns at the second session, Week 2.

Both groups will then follow up and be given diet and exercise education handouts and instruction based on the DPP GLB core nutrtion and physical activity materials (Appendix B) at Week 2. The diabetes and prediabetes CGM intervention groups will also receive additional education on how food and exercise affects bloods sugar, and how to evaluate and respond to their blood sugar changes with RT-CGM (Appendix A). The CGM intervention participants will then wear the RT-CGM device for 10 days at week 2 and at 6 weeks. At week 2, CGM patterns will be reviewed with diet and food logs, and CGM intervention patients will be challenged "to beat their averages. The control group will review their diet and exercise log with the instructor and attempt to continue to make small changes in diet and exercise. Vital signs will be taken at each visit, including waist circumference. Pedometer data will be collected at weeks 6 and 14. Week 2 education on nutrition and RT-CGM will take 1 hour 30 minutes to 2 hours. Week 6 CGM review and measurements will take 1 hour. They will mail their sensors back from the continuous glucose monitoring device after 10 days, along with physical activity and food logs. They continue wearing their pedometers during this time.

Page 8 of 14

#### Week 14

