Title: A	Pilot Study on the Use of Real-Time Continuous G	ilucose Monitoring	(RT-CGM) as a	Tool for Weig	ht
Lo	ss/Behavior Modification in Patients with Prediab	etes and Diabetes			

NCT #: 03805412

Date: 18 November 2018

Initial statistical analysis

Sample Size Justification and data analysis: In order to establish stable estimates of effect sizes, we anticipate using a total sample size of N=30 patients (15 prediabetes, 15 Type 2 diabetes). Data will be analyzed using mixed model regression, which accounts for within subject correlation. The relevant effect size for each outcome will be the time main effect. As a secondary analysis, we plan to examine predictors of change using general linear models. This will help us determine the type of patient for whom the CGM intervention is most effective, which can inform the patient selection process in later studies. Predictors of interest include diagnosis (diabetes vs prediabetes), comorbidities, demographics (age, sex, race, type of insurance), BMI, and pre-intervention attitudes (toward diet, activity, and exercise changes)

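### The SAP's time main effect in 30 patients gives Aim 3 an uncontrolled before-after change, and the SAP does not say which CGM sessions define it

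*Protocol*

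**What the plan says.** Aim 3 (Protocol, Specific Aims) is to evaluate what RT-CGM does to glycemic variability in prediabetes and diabetes. The CGM data paragraph lists SD, MAGE and other variability measures, which "with be reviewed from the CGM device data at baseline 2, 6 and 14 weeks". It names no comparison.

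The sessions behind those four time points are:

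- **Week 0:** both arms "will be asked to wear the CGM blinded for 10 days" (Screening/Pre-Intervention Visit).
- **Weeks 2 and 6:** "The CGM intervention participants will then wear the RT-CGM device for 10 days at week 2 and at 6 weeks". No control-arm CGM is described at these visits.
- **Week 14:** both arms again wear a blinded sensor for 10 days (Week 14).

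The lifestyle material is common to the arms: "Both groups will then follow up and be given diet and exercise education handouts and instruction" (Weeks 2, 6).

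On numbers, the Protocol has an intervention arm of 30 ("All those enrolled in the CGM intervention (N=30) will participate in 2 cycles of RT-CGM") and a randomised control arm: "15 subjects will be in the control group with either prediabetes (n=7) or diabetes (n=8". The SAP says "we anticipate using a total sample size of N=30 patients (15 prediabetes, 15 Type 2 diabetes". It specifies mixed model regression and states: "The relevant effect size for each outcome will be the time main effect". It has no arm term, no arm-by-time term, no time coding and no reference visit. Arm is also absent from its list of secondary predictors of change.

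**The concern.** Two gaps meet in Aim 3.

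The first is the missing control. A time main effect in the CGM arm is a before-after change. Both arms receive the condensed lifestyle programme, so a fall in variability could come from counselling, from self-recording or from regression to the mean. None of these can be separated from RT-CGM without the control arm, which the trial randomises and the SAP does not use.

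The second is particular to the CGM outcomes. Two of the four sessions are read while the participant can see the glucose display, and two while they cannot. A change seen on display and a change still present at a blinded session weeks later answer different questions. The SAP does not choose between them.

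The SAP says its purpose is stable effect-size estimates, and it looks ahead to later studies. An effect size that includes the counselling effect, or that depends on an unstated choice of sessions, could mislead the planning of those studies.

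**Working it through.** **1. The plan's own numbers.** The SAP's 30 is 15 + 15. The Protocol's total is 15 + 15 + 15 = 45, or by diagnosis 15 + 7 = 22 prediabetes and 15 + 8 = 23 diabetes, as its Confidentiality section states. Each document adds up, and the two differ by exactly the 15 controls. The SAP gives no effect size, SD, power or precision target, so 30 cannot be derived from a formula.

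**2. What a time effect estimates.** Let the mean change from week 0 to week 14 be Δ1 in the CGM arm and Δ0 in controls. The controlled effect is Δ1 − Δ0.

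- CGM arm only: the time effect is Δ1.
- All 45 without an arm term: it is (30Δ1 + 15Δ0)/45 = (2Δ1 + Δ0)/3.

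If both arms fall by 5 mg/dL, both versions give −5 while the controlled effect is 0.

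**3. How the sessions and coding matter (illustrative; no document gives the profile).** Suppose variability falls by d at weeks 2 and 6, and a share p of the fall remains at week 14. The means at weeks 0, 2, 6, 14 are then 0, −d, −d, −pd.

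- Post-baseline average: −(2 + p)d/3.
- Linear in weeks: the mean week is 5.5, the deviations are −5.5, −3.5, 0.5 and 8.5, and their sum of squares is 115. The slope is (3.5 − 0.5 − 8.5p)d/115 = (3 − 8.5p)d/115 per week, multiplied by 14 for the whole period.
- Linear in visit number: slope −0.3pd, or −0.9pd over three steps.
- Categorical, week 14 minus week 0: −pd.

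| p | Post-baseline average | Linear in weeks | Linear in visit | Week 14 − week 0 |
|---|---|---|---|---|
| 0 | −0.67d | +0.37d | 0 | 0 |
| 0.5 | −0.83d | −0.15d | −0.45d | −0.50d |
| 1 | −d | −0.67d | −0.90d | −d |

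The size of the effect moves with the choice.

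**4. Precision of the controlled contrast.** The SDs are the background MAGE values in Preliminary Studies: 18 mg/dL (prediabetes) and 28 mg/dL (diabetes). The correlation r between week 0 and week 14 is assumed to be 0.3 to 0.7. The low end of each range uses SD 18 and r = 0.7; the high end uses SD 28 and r = 0.3. Also √(1/30 + 1/15) = 0.316.

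- SD of change = SD × √(2(1 − r)): 18 × √0.6 = 13.9; 28 × √1.4 = 33.1.
- Uncontrolled paired change, n = 30: t(29) = 2.045; 2.045 × 13.9/√30 = **5.2** to 2.045 × 33.1/√30 = **12.4** mg/dL.
- Between-arm difference in change, 30 vs 15: t(43) = 2.017; 2.017 × 13.9 × 0.316 = **8.9** to 2.017 × 33.1 × 0.316 = **21.1** mg/dL.
- Like-for-like ratio: 8.9/5.2 and 21.1/12.4, each about **1.7**.
- Adjusted for baseline and diagnosis: residual SD = SD × √(1 − r²); t(41) = 2.020; 2.020 × 12.9 × 0.316 = **8.2** to 2.020 × 26.7 × 0.316 = **17.1** mg/dL.
- The same with 20 vs 10 completers (near the 35% drop-out in the team's earlier lifestyle pilot): t(26) = 2.056, √(1/20 + 1/10) = 0.387, giving **10.2** to **21.3** mg/dL.

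**The case against.** The best defence is that this is a pilot with a short SAP, headed as an initial analysis, and that the missing control arm affects weight and activity as much as Aim 3. Both statements are right. The first excuses the lack of a power calculation. It does not excuse an effect size that cannot answer the aim, since estimating effect sizes is what the SAP says the sample is for. The second means that the arm term and the N should be corrected for every outcome; the session question remains particular to the CGM measures. The SAP may predate the control arm, but neither document says so.

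A second defence is that week 14 is not the only legitimate target. Aim 3 gives no time point, and an on-display effect at weeks 2 and 6 is a fair reading of it. This stands. The reason to prefer week 14 is practical: it is the only post-baseline visit at which both arms have CGM data.

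Third, the between-arm contrast does not isolate the display either. The CGM arm also receives added education on glucose responses, review of its patterns and a challenge to improve on them. This stands too and limits what the fix can claim.

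A reader might infer three stronger points that the documents do not support:

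- **The SAP pools blinded and on-display sessions.** No text says so. The Protocol lists when the measures are reviewed, and the SAP leaves the sessions open.
- **The plan would get the sign of the effect wrong.** In the illustration this happens only under linear-in-weeks coding with less than 3/8.5 = 35% of the fall persisting, on a profile that was made up. At p = 0 there is no week-14 sign to reverse.
- **Categorical visit coding would not help because its overall test has no direction.** The SAP asks for an effect size, and single visit coefficients do have a direction. What is missing is which one to report.

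**Conclusion.** The concern holds. Followed as written, the SAP yields a before-after change for Aim 3 that cannot be credited to RT-CGM, and it leaves open which sessions and contrast define that change. That the SAP's 30 are the CGM arm is an inference from the matching 15 + 15, but the conclusion does not depend on it: with all 45 and no arm term, the time effect is still an average over arms.

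The omission is certain from the text. Its numerical consequence is not, because the time profiles and correlations are assumptions and the SDs are background figures rather than design inputs. The SAP should be corrected. The fault lies in the analysis plan, since the design already collects the blinded data that a controlled estimate needs.

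**What to change.** Replace the SAP's effect definition for Aim 3 with text such as:

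> The main Aim 3 effect is the between-arm difference (RT-CGM package vs control) in MAGE at the week-14 blinded session, adjusted for the week-0 blinded value and diagnosis, in all randomised participants (30 vs 15) with available data, with a 95% CI. SD of glucose is analysed the same way as a supporting measure. Weeks 2 and 6 are reported separately as on-display, uncontrolled changes from week 0 in the CGM arm.

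Correct the SAP's N from 30 to 45.

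**Cost.** No new visits or measurements are needed, since both arms already wear both blinded sessions. The analysed set grows by the 15 controls, and weeks 2 and 6 leave the main estimate but are still reported. The price is precision: like for like, the interval is about 1.7 times as wide as that of the uncontrolled change. Baseline adjustment recovers part of this, and dropout would take some of it back. State the expected width in the SAP. Present the result as a planning estimate of the whole package (display, added education and pattern review), not as a test and not as the effect of the display alone.
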